4.2.2 SECONDARY PERFORMANCE ENDPOINTS

- Improvement in appearance of surgical scars at 1 and 2 months post-treatment as evaluated by independent blinded reviewer using the General Aesthetic Improvement Scale (GAIS) and Manchester Scar Scale (MSS).
- Assessment of surgical scars at 3 and 10 months post-treatment as evaluated by independent blinded reviewer using the Patient and Observer Scar Assessment Scale (POSAS).
- Assessment of surgical scars at 3 and 10 months post-treatment as evaluated by the subject using the Patient and Observer Scar Assessment Scale (POSAS).
- Subjects' assessment of satisfaction (5-point Likert Scale) with the treatment at 3 and 10 months post-treatment.

Safety endpoints:

- Subject's assessment of discomfort and pain after treatment as measured by a 10 cm visual analog scale (VAS).
- Subjects experiencing a treatment-related adverse event (AE) by 10 months post-treatment.

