7.3.2 ENROLLMENT/BASELINE

Enrollment/Baseline Visit (Visit 2, Day 0)

Once a subject has been confirmed that they continue to meet inclusion/exclusion criteria, they will receive a unique identifying number that will be composed of a two-digit site number and a two-digit subject number in sequence. This unique identifier will be used throughout the entire study and will be entered in the subject's case report form (CRF). The investigator will confirm that the subject still meets the inclusion/exclusion criteria. Vital signs and demographics will be collected and a physical exam will be performed. The subject will complete the POSAS.

Photography

Photographs will be taken prior to first treatment and throughout the study according to specified time points detailed in the Schedule of Events Table (section 7.3.7), utilizing standard scientific equipment. Two sets of photographs will be required, one set for the treated side of the body/face and a second set for the untreated side of the body/face.

The photos should be taken in a private room or area of the clinic under controlled conditions, including the distance, angle, background and lighting in order to achieve high-quality sets of photographs. Direct illumination will not be used. The subject should be placed in the same position each time. As each photograph is taken, it should be viewed to ensure that it is in focus and is similar to its baseline counterpart in all technical aspects, including lighting, distance and angle.

For consistency purposes, the same person should ideally take all study photographs, especially per subject. The digital files should follow a consistent standard naming scheme.

Treatment

Subjects will receive treatment as described in section 7.3.1. Only one side of the body/face will be treated. The same side will be treated for the duration of the study. Only half of a scar will be treated

and remaining half will serve as the control. Following treatment, the investigator will examine the treated area and report immediate and short term response. Subjects will complete the 10 cm discomfort/pain VAS immediately after treatment. A new disposal tip will be used for each patient treatment.

Treatment procedure should include positioning of the patient in a manner that enables comfortable access to the treated anatomical site.

Assessment

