
Subjects will return to the clinic one month after the last assessment. Adverse events, vital signs and any changes to concomitant medications will be recorded.

Photographs of the treated area will be taken as described in section 7.3.1. Subjects will be discharged from the clinic and will be instructed to return for the Month 5 assessment.

Visit 10, Month 5 (\pm 7 days)

Subjects will return to the clinic one month after the last assessment. Adverse events, vital signs and any changes to concomitant medications will be recorded. Subjects will complete a 5-point Likert satisfaction questionnaire and the POSAS.

Photographs of the treated area will be taken as described in section 7.3.1. Subjects will be discharged from the clinic and will be instructed to return for the final Month 12 assessment.

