7.3.7 SCHEDULE OF EVENTS TABLE

Procedures	Screening/Baseline (Visit 1, Day -1)	Enrollment/Treatment (Visit 2, Day 0)	Follow-up (Visit 3, Day 0+2 days)	Treatment & Follow-up (Visit 4, Month 1 (± 7 days))	Follow-up (Visit 5, Month 1+2 days)	Treatment & Follow-up (Visit 6, Month 2 (± 7 days))	Follow-up (Visit 7, Month 2+2 days)	Follow-up (Visit 8, Month 3 (± 7 days))	Follow-up (Visit 9, Month 4 (± 7 days))	Follow-up (Visit 10, Month 5 (± 7 days))	Final Study Visit (Visit 11, Month 12 (± 14 days))
Informed consent	X										
Inclusion/exclusion criteria	X	X									
Demographics	X										
Medical history	X										
Physical exam	X										
Vital signs		X	X	X	X	X	X	X	X	X	X
Urine pregnancy test ^a	X										
Test Spot	X										
Photographs		X						X	X	X	X
Administer Treatment		X		X		X					
Discomfort/Pain VAS	X		X		X						
PI immediate & short-term response	X		X		X						
Blinded reviewer GAIS		X						X	X	X	X
Blinded reviewer MSS	X							X	X	X	X
Blinded reviewer POSAS	X									X	X
Subject POSAS	X									X	X
Subject satisfaction questionnaire										X	X
Concomitant medication	X	X	X	X	X	X	X	X	X	X	X
Adverse event evaluation		X	X	X	X	X	X	X	X	X	X

Procedures	Screening/Baseline (Visit 1, Day -1)	Enrollment/Treatment (Visit 2, Day 0)	Follow-up (Visit 3, Day 0+2 days)	Treatment & Follow-up (Visit 4, Month 1 (± 7 days))	Follow-up (Visit 5, Month 1+2 days)	Treatment & Follow-up (Visit 6, Month 2 (± 7 days))	Follow-up (Visit 7, Month 2+2 days)	Follow-up (Visit 8, Month 3 (± 7 days))	Follow-up (Visit 9, Month 4 (± 7 days))	Follow-up (Visit 10, Month 5 (± 7 days))	Final Study Visit (Visit 11, Month 12 (± 14 days))
^a For women of child-bearing potential.											

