 - **Null Hypothesis ($H_0: \mu_d = \mu_{post} - \mu_{pre} = 0$)** – There is no improvement of surgical scars at 3 and 10 months post-treatment review compared to baseline.
Alternative Hypothesis ($H_a: \mu_d = \mu_{post} - \mu_{pre} \neq 0$) – There is improvement of surgical scars at 3 and 10 months post-treatment review compared to baseline. The improvement of surgical scars will be defined using Patient and Observer Scar Assessment Scale (POSAS) scores evaluated by the subject.
 - **Null Hypothesis ($H_0: \mu_d = \mu_{post} - \mu_{pre} = 0$)** – There is no satisfaction with treatment as documented on a 5-point Likert scale at 3 and 10 months compared to baseline.
Alternative Hypothesis ($H_a: \mu_d = \mu_{post} - \mu_{pre} \neq 0$) – There is satisfaction with treatment as documented on a 5-point Likert scale at 3 and 10 months compared to baseline. The satisfaction with treatment will be defined by 5-point Likert scale at 3 and 10 months compared to baseline as assessed by the subjects.
- Safety Endpoint:
 - **Null Hypothesis ($H_0: \mu_d = \mu_{post} - \mu_{pre} = 0$)** – There is no difference in subjects' 10 cm discomfort/pain VAS score experienced after at Visit 6 treatment and that of baseline treatment (Visit 2).
Alternative Hypothesis ($H_a: \mu_d = \mu_{post} - \mu_{pre} \neq 0$) – There is a difference in subjects' 10 cm discomfort/pain VAS score experienced after at Visit 6 treatment and that of baseline treatment (Visit 2). Expected mean difference is maximum VAS score ≤ 1 .

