10.4 DESCRIPTION OF STATISTICAL METHODS

10.4.1 GENERAL APPROACH

All summary tables for quantitative parameters will display mean, standard deviation, median, range (minimum and maximum), percentages as well as number of missing data (if relevant). All summary tables for qualitative parameters will display counts, percentages and number of missing data if relevant. Baseline data are defined as the last measurement performed before the first treatment on Visit 2.

All statistical tests will be two-sided. The level of statistical significance for effectiveness analyses is 5% ($\alpha = 0.05$) for all tests of differences. Where appropriate, Paired t-test and/or Wilcoxon Signed-Ranks Test for Matched Pairs will be used to compare the evaluations at the baseline and post treatment sessions. This test will enable us to accept or reject the null hypotheses. Rejection of null hypotheses will establish that:

- The two-sided 95% confidence interval for the difference between the means excludes zero.
- The two means are statistically significantly different at the 5% level ($P < 0.05$) two-sided.

Upon rejection of null hypotheses, further statistical test tools such as Confidence Interval and/or t-test will be used to determine the performance of Venus Viva™ fractional RF System in the treatment of surgical scars following breast augmentation, abdominoplasty or face lift.

In order to accommodate imbalances of some baseline General Aesthetic Improvement Scale (GAIS) and Manchester Scar Scale (MSS) scores, covariate adjustment analysis may be performed in SAP to estimate adjusted treatment effects for the primary endpoint analysis.

The assumption for the statistical test is that the paired differences of baseline and post treatment data are normally distributed.

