10.4.3 ANALYSIS OF THE SECONDARY ENDPOINT(S)

For the analysis of GAIS, MSS, POSAS and 5-point Likert scale secondary performance endpoints, the following analysis will be considered:

- Summary tables for differences of 1 and 2 month post treatment GAIS and MSS scores compared to baseline as evaluated by independent blinded reviewer will be displayed as mean difference, standard deviation and standard error. The point level for each of these ordinal scale assessment tools will be put into consideration where applicable.

Summary tables for differences of 3 and 10 month post treatment POSAS score compared to baseline as evaluated by independent blinded reviewer and the subjects will be displayed as mean difference, standard deviation and standard error. The point level for each of these ordinal scale assessment tools will be put into consideration where applicable.

Similarly, summary tables of 5-point Likert scale satisfaction scores assessed by the subjects at 3 and 10 month post treatment visits as well as differences between satisfaction scores at 10 months compared to 3-month post treatment visits will be displayed as mean, mean difference, standard deviation and standard error. The point level for each of these ordinal scale assessment tools will be put into consideration where applicable.

- Where applicable, bar charts, pie chart, graphs or any other descriptive statistical displays indicating scores, percentages or proportions of subjects' GAIS, MSS, POSAS and 5-point Likert scale improvement and satisfaction scores will be used to analyse performance.

- All statistical tests that will be two-sided. The level of statistical significance for effectiveness analyses is 5% ($\alpha = 0.05$) for all tests of differences. Where appropriate, Paired t-test and/or Wilcoxon Signed-Ranks Test for Matched Pairs will be used to compare the evaluation of score differences of GAIS, MSS, POSAS and 5-point Likert scale post treatment assessment. Analysis of Covariance (ANCOVA) may also be used where appropriate.

GAIS, MSS, POSAS and 5-point Likert scale scores of all subjects who received at least one treatment of Venus Viva™ system for the treatment of surgical scars following breast augmentation, abdominoplasty or face lift and for whom at least one valid post-baseline assessment were obtained will be analysed for these secondary endpoints. Multiple imputation method or modelling of available data may be used for missing data as appropriate.

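### The satisfaction hypothesis in section 10.2 is a change from baseline, but satisfaction is collected only after treatment, so the stated paired test cannot be run

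*Combined protocol and SAP*

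**What the plan says.** Section 10.2 gives satisfaction the same template as the scar scales: a null of zero mean difference (post minus pre) and a two-sided alternative. The null is worded "There is no satisfaction with treatment as documented on a 5-point Likert scale at 3 and 10 months compared to baseline", and the alternative repeats the comparison: "The satisfaction with treatment will be defined by 5-point Likert scale at 3 and 10 months compared to baseline as assessed by the subjects". Section 10.4.1 fixes what baseline means: "Baseline data are defined as the last measurement performed before the first treatment on Visit 2".

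The endpoint itself, in section 4.2.2, has no baseline component: "Subjects' assessment of satisfaction (5-point Likert Scale) with the treatment at 3 and 10 months post-treatment".

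Section 10.4.3 plans tables of the satisfaction scores at the 3-month and 10-month visits, together with "differences between satisfaction scores at 10 months compared to 3-month post treatment visits". Where applicable, it also plans charts or other displays of scores, percentages or proportions. Paired t-tests and/or Wilcoxon signed-rank tests are to be used where appropriate.

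**The concern.** A paired test needs two measurements per subject. Section 10.2 requires one of them before the first treatment, and the visit schedule never collects it. Nor could a baseline questionnaire supply it, because satisfaction with a treatment has no meaning before the treatment is given.

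Two analysts could then diverge. One following section 10.2 has nothing to compute. One following section 10.4.3 might take the 10-month against 3-month difference as the test of the hypothesis. That difference answers another question, and its result could be reported under the wording of section 10.2 as evidence for or against satisfaction. With no definition of a satisfied subject in the plan, the replacement analysis would be chosen after the scores are known.

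**Working it through.** There is no sample size, effect size or power statement for satisfaction in the documents, so there is no figure to reproduce. The check sets the sections side by side.

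**1. Timing of the visits.** The last treatment is at Visit 6, Month 2 (section 7.3.3). Visit 10 is at Month 5, and 5 − 2 = 3 months post-treatment. Visit 11 is at Month 12, and 12 − 2 = 10 months post-treatment. These are the two time points named in the endpoint.

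**2. Where satisfaction is collected.**

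| Source | Satisfaction |
|---|---|
| 7.3.2, Visit 2 (baseline) | Not mentioned; the only scale the subject completes before treatment is given by "The subject will complete the POSAS" |
| 7.3.3, Visit 10 | Collected: "Subjects will complete a 5-point Likert satisfaction questionnaire and the POSAS" |
| 7.3.4, Visit 11 | Collected, in the same words |
| 7.3.5, early termination | Repeats Visit 11, so post-treatment only |
| 7.3.7, row "Subject satisfaction questionnaire" | Two marks, in the columns for Visits 10 and 11 |
| 10.4.6, baseline statistics | GAIS, MSS and POSAS; satisfaction not listed |

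Some other rows of the schedule table appear shifted in the extracted text, so the conclusion rests on the visit descriptions. The satisfaction row agrees with them.

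**3. Pairs available.** Baseline measurements scheduled: 0. Post-treatment measurements scheduled: 2. Pre/post pairs per subject: 0, for the 3-month comparison and for the 10-month comparison alike. Neither the baseline mean nor the mean difference in section 10.2 can be estimated. Section 10.4.3 allows multiple imputation, but a variable that is unobserved in every subject cannot be imputed from these data.

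**4. The one paired contrast that can be formed.** It is Visit 11 minus Visit 10. Suppose, for illustration, that scores run from 1 (worst) to 5 (best):

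- every subject scores 5 at both visits: each difference is 5 − 5 = 0;
- every subject scores 1 at both visits: each difference is 1 − 1 = 0.

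The contrast cannot tell these two trials apart. If scores fell between the visits, a two-sided test could reject zero difference. Read against section 10.2, that rejection would support the alternative that there is satisfaction, although satisfaction had declined.

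**The case against.** The strongest reply is that little is lost in practice. The endpoint in section 4.2.2 is an assessment of satisfaction and does not itself call for a test. Section 10.4.3 plans the mean, standard deviation and standard error at each visit and allows for proportions, so the level of satisfaction can be reported. The paired tests are qualified by where appropriate, and the baseline phrase looks like wording carried over from the other hypotheses in section 10.2.

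Most of this stands. A reader might infer that the endpoint cannot be analysed at all, or that the 10-month against 3-month difference is the only analysis available. The documents do not support either reading: the per-visit summaries are planned, and a one-sample analysis at each visit can be run on the data collected. A reader might also infer damage to the trial's main conclusion. Section 10.4.2 bases success on GAIS and MSS, and section 10.5 sizes the study on GAIS at 3 months, so satisfaction enters neither.

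The reply does not remove the contradiction. Section 10.2 still states a hypothesis that cannot be tested, section 10.4.3 does not replace it with one that addresses satisfaction, and neither section says which scores count as satisfied.

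**Conclusion.** The point holds as an inconsistency between section 10.2 and the rest of the plan. The stated satisfaction test has no pre/post pairs by design and cannot be run. The paired contrast in section 10.4.3 measures durability and does not stand in for it.

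The consequence is limited to one secondary endpoint. Descriptive reporting remains possible; what is missing is a runnable hypothesis and a prespecified definition of satisfied. No numerical size beyond the count of pairs can be given, because the documents state no expected distribution of satisfaction scores.

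The conclusion about the test rests on the visit text alone. The remedy rests on one assumption: that the 5-point scale has a midpoint that means neutral and identifiable satisfied categories. The documents do not give the anchors.

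**What to change.** - In section 10.2, delete the baseline comparison from the satisfaction null, alternative and definition.
- Make the analysis the proportion of subjects in the satisfied categories at 3 and at 10 months post-treatment, each with an exact 95% confidence interval.
- If a test is wanted, specify a one-sample signed-rank test against the scale midpoint at each visit.
- In section 10.4.3, label the 10-month against 3-month difference as durability of satisfaction.
- Write out the Likert anchors, the satisfied categories and the midpoint before database lock.

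The cost is small, though it goes beyond a change to the SAP alone. Section 10.1 allows a revised SAP before database lock, but the hypothesis sits in section 10.2 of the combined document, and section 13.2 requires ethics committee or IRB approval of any protocol amendment. No new data, visits or subjects are needed.

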10.3 ANALYSIS DATASETS

Modified Intention-to-Treat Analysis Dataset will be used; performance and safety analyses will be carried out on all subjects who received at least one treatment of Venus Viva™ system and for whom at least one valid post-baseline performance and safety evaluation were obtained.

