I will conduct the trial in accordance with the clinical investigation plan, Good Clinical Practice guidelines, ISO 14155:2011 (Clinical Investigation of Medical Devices for Human Subjects - Good Clinical Practice), as well as local regulations. I also accept respective revisions to the clinical investigation plan approved by authorized personnel of the Sponsor and by regulatory authorities.

Institution:

[name] [name]

Principal Investigator (Printed name)

Principal Investigator (Signature)

22/2/18

Date

PROTOCOL SUMMARY

TITLE	Clinical Evaluation of the Safety and Performance of Fractional RF for the Treatment of Surgical Scars Following Breast Augmentation, Abdominoplasty or Face Lift
SUMMARY	Split-body/face evaluator-blind study of the safety and performance of fractional RF for the treatment of surgical scars following breast augmentation, abdominoplasty or face lift. The study will enroll up to 50 female subjects requesting treatment of surgical scars following breast augmentation or abdominoplasty and up to 25 male and female subjects requesting treatment of surgical scars following face lift surgery. Subjects will receive a total of three treatments of their surgical scars at one-month intervals on one side of the body or facial incision only. Subjects will be followed up at one, two, three and ten months after their last treatment. Analysis will be performed on all subjects who receive at least one treatment. Outcomes will be compared to the non-treated side.
OBJECTIVES	The objective of this clinical study is to evaluate the safety and performance of fractional RF for the treatment of surgical scars following breast augmentation, abdominoplasty or face lift.

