5.5 PARTICIPANT WITHDRAWAL OR TERMINATION

5.5.1 REASONS FOR WITHDRAWAL OR TERMINATION

Subjects are free to withdraw from participation in the study without prejudice at any time upon request. In the event that a subject drops out of the study or is withdrawn from the study, the End of Study/Early Discontinuation CRF form should be completed. On the discontinuation page, the Investigator should record the date of the withdrawal and the reason for withdrawal.

Reasonable effort should be made to contact any subject lost to follow up during the course of the study in order to complete assessments and retrieve any outstanding data. The records of subjects who terminate prior to completing the study will be retained and the reason for termination will be documented.

The investigator may terminate participation in the study if:

- Any clinical adverse event (AE), laboratory abnormality, or other medical condition or situation occurs such that continued participation in the study would not be in the best interest of the subject.
- The subject meets an exclusion criterion (either newly developed or not previously recognized) that precludes further study participation.

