5.5.2 HANDLING OF PARTICIPANT WITHDRAWALS OR TERMINATION

Every effort will be made to continue follow-up of withdrawn or terminated subjects or subjects who discontinue the intervention but remain in the study for follow-up, especially for safety and performance study endpoints. Every effort will be made to conduct an exit visit (final study visit, see section 7.3.5) to withdrawn patients, and to undertake protocol-specified safety follow-up procedures to capture AEs, serious adverse events (SAEs) and device deficiencies.

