The investigator will examine the treated areas and report immediate and short term response (30 minutes post-treatment) (pain during treatment, hemorrhage, burn, erythema, edema, purpura) using a 5-point scale: 1=none; 2=trace; 3=moderate; 4=marked; 5=severe.

The assessment of discomfort/pain based on the subject's completion of the 10 cm VAS should also be documented immediately after each treatment.

The normal response to these treatments is transient erythema and edema. If any other side effects occur, as indicated in the protocol, they must be recorded.

Subjects will be discharged from the clinic and will be instructed to return in 2-3 days in order to be examined for adverse events.

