7.3.3 FOLLOW-UP

Visit 3, Day 0+2 days

Subjects will be examined 2-3 days after treatment for the occurrence of adverse events. Vital signs and any changes in concomitant medication will be recorded. Subjects will be discharged from the clinic and will be instructed to return for the Month 1 assessment and treatment.

Visit 4, Month 1 (\pm 7 days)

Subjects will return to the clinic one month after the first treatment. Adverse events, vital signs and any changes to concomitant medications will be recorded.

Subjects will receive treatment as described in section 7.3.1. Following treatment, the investigator will examine the treated area and report immediate and short term response. Subjects will complete the 10 cm discomfort/pain VAS immediately after treatment.

Subjects will be discharged from the clinic and will be instructed to return in 2-3 days in order to be examined for adverse events.

Visit 5, Month 1+2 days

Subjects will be examined 2-3 days after treatment for the occurrence of adverse events. Vital signs and any changes in concomitant medication will be recorded. Subjects will be discharged from the clinic and will be instructed to return for the Month 2 assessment and treatment.

Visit 6, Month 2 (\pm 7 days)

Subjects will return to the clinic one month after the second treatment. Adverse events, vital signs and any changes to concomitant medications will be recorded.

Subjects will receive treatment as described in section 7.3.1. Following treatment, the investigator will examine the treated area and report immediate and short term response. Subjects will complete the 10 cm discomfort/pain VAS immediately after treatment.

Subjects will be discharged from the clinic and will be instructed to return in 2-3 days in order to be examined for adverse events.

Visit 7, Month 2+2 days

Subjects will be examined 2-3 days after treatment for the occurrence of adverse events. Vital signs and any changes in concomitant medication will be recorded. Subjects will be discharged from the clinic and will be instructed to return for the Month 3 assessment.

Visit 8, Month 3 (\pm 7 days)

Subjects will return to the clinic one month after the third treatment. Adverse events, vital signs and any changes to concomitant medications will be recorded.

Photographs of the treated area will be taken as described in section 7.3.1. Subjects will be discharged from the clinic and will be instructed to return for the Month 4 assessment.

Visit 9, Month 4 (\pm 7 days)

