7.3.5 EARLY TERMINATION VISIT

Subjects who terminate the study early for whatever reason, will be asked to return to the clinic, if they are willing, to complete the final visit (Visit 11). Adverse events and the reason for early termination will be recorded.

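### Section 10.3 has one dataset for performance and safety; read literally, it keeps treated subjects out of the safety summaries unless they have a post-baseline performance evaluation

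*Combined protocol and SAP*

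**What the plan says.** Section 10.3 (Analysis Datasets) is the only place where an analysis population is defined. It names one modified intention-to-treat set for both performance and safety. Membership requires at least one treatment, and the set is limited to subjects "for whom at least one valid post-baseline performance and safety evaluation were obtained".

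The Protocol Summary gives a different rule with no evaluation condition: "Analysis will be performed on all subjects who receive at least one treatment".

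Sections 10.4.2 and 10.4.3 restate the evaluation condition for performance only, by endpoint: post-baseline GAIS and MSS for the primary endpoint, and a post-baseline assessment for the secondary endpoints. Section 10.4.4 (Safety Analyses) reports numbers and percentages of subjects with any AE, with any serious AE and withdrawn from treatment because of an AE. It also covers the investigator's immediate and short-term response reports and a paired comparison of the pain VAS at Visits 2 and 6. It names no analysis set.

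Safety data begin on the first treatment day. Section 7.3.2 says "Subjects will complete the 10 cm discomfort/pain VAS immediately after treatment", and the investigator also records the response at that visit. Performance data begin again only at Visit 8, for which section 7.3.3 says "Subjects will return to the clinic one month after the third treatment".

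**The concern.** The wording of 10.3 joins the two evaluations with 'and', and applies the joint condition to both kinds of analysis. Taken as written, a subject with complete safety records but no post-baseline performance evaluation is not in the set on which safety is analysed.

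This could matter because the exclusion may depend on the outcome. Section 5.5.1 lets the investigator end participation if "Any clinical adverse event (AE), laboratory abnormality, or other medical condition or situation occurs such that continued participation" would not be in the subject's interest. A subject who stops for an AE during the treatment phase and does not come back is a likely person to lack a performance evaluation. The row for withdrawal from treatment due to an AE is the most exposed, because all treatment ends at Visit 6, before the first scheduled post-baseline performance evaluation.

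The conflict with the Protocol Summary is a problem in its own right. Two analysts following different sections could report different safety denominators from the same data.

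**Working it through.** **Step 1. What is scheduled before and after Visit 8** (sections 7.3.2 to 7.3.5 and 7.3.7)

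- Visits 2, 3, 4, 5, 6 and 7 (six visits): AE evaluation. Pain VAS and investigator response follow each treatment, at Visits 2, 4 and 6. No post-baseline performance evaluation.
- Visit 8 (Month 3): first follow-up photographs and first post-baseline blinded GAIS and MSS.
- Visit 10 (Month 5): first post-baseline POSAS and satisfaction questionnaire.
- Early leavers: a voluntary exit visit that repeats Visit 11. It can yield a blinded rating from photographs, a subject POSAS or a satisfaction score. Each is a performance endpoint under 4.2, so any one of them could meet the condition in 10.3.

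**Step 2. Who is in the safety analyses under each reading**

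| Subject | Analysis | 10.3 literal | 10.3 'respectively' | All treated |
|---|---|---|---|---|
| Leaves after Visit 2, before the Visit 6 VAS, no performance evaluation | AE, SAE, AE-withdrawal, response | out | in | in |
| Same | Paired VAS | no pair | no pair | no pair |
| Leaves after the Visit 6 VAS, before Visit 8, no performance evaluation | AE, SAE, AE-withdrawal, response | out | in | in |
| Same | Paired VAS | out | in | in |
| Any performance evaluation at Visit 8 or later, or at exit | AE, SAE, AE-withdrawal, response | in | in | in |

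The readings differ only for subjects without a performance evaluation. For the VAS test they differ only for those lost between Visits 6 and 8.

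**Step 3. What the documents allow on numbers**

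The plan gives no figure for early loss. The nearest is the allowance in 10.5, where 11 × 1.3 = 14.3 is rounded up to 15 per cohort. Maximum enrolment is 50 + 25 = 75. Taken as 30% of those enrolled, the allowance is 75 × 0.30 = 22.5. Taken as the inflation actually used, the loss is 1 − 1/1.3 = 3.3/14.3 = 23.1%, and 75 × 0.231 = 17.3. Both cover the whole study, so neither counts early leavers. If, as an assumption, a 30% loss were spread evenly over 12 months with no exit evaluations:

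- before Month 3: 22.5 × 3/12 = 5.6, about 6 subjects;
- between Months 2 and 3: 22.5 × 1/12 = 1.9, about 2 subjects.

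**Step 4. Effect on AE summaries (all counts and rates assumed)**

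Suppose the only AE withdrawals are among subjects without a performance evaluation, and everyone else is in the set. Clopper-Pearson 95% intervals, with upper limit 1 − 0.025^(1/n) when the count is zero:

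| Such withdrawals | Literal 10.3 | All treated |
|---|---|---|
| 0 | 0/75 | 0/75 |
| 1 | 0/74 = 0% (0 to 4.9%) | 1/75 = 1.3% (0.03 to 7.2%) |
| 3 | 0/72 = 0% (0 to 5.0%) | 3/75 = 4.0% (0.8 to 11.2%) |

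For any-AE rates, take 69 retained subjects with a 10% rate and 6 early leavers with rate p. The all-treated rate is (69 × 0.10 + 6p)/75, and the literal set reports 10%.

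- p = 10%: 7.5/75 = 10.0%, no bias.
- p = 50%: 9.9/75 = 13.2%.
- p = 100%: 12.9/75 = 17.2%.

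**Step 5. Effect on the paired VAS mean (assumed)**

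Let N subjects have both values, and let k excluded subjects have a mean change D cm above the rest. Excluding them lowers the mean by kD/N. With N = 75:

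- k = 1, D = 2: 0.027 cm;
- k = 3, D = 2: 0.080 cm;
- k = 3, D = 4: 0.160 cm;
- k = 0 or D = 0: no shift.

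The plan's mark for this difference is 1.

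**The case against.** The best reply is that 10.3 pairs performance and safety analyses with performance and safety evaluations, and so means each evaluation for its own analysis. Sections 10.4.2 and 10.4.3 apply the rule that way, and the Protocol Summary points to all treated subjects. Under that reading almost no one is excluded from safety, because VAS and response data follow the first treatment. This is plausible and cannot be ruled out. But 10.3 does not say it, and the sections that support it concern performance only. Section 10.4.4 has no parallel sentence.

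A second reply is that AE leavers are the ones most actively pursued. Section 5.5.2 says "Every effort will be made to continue follow-up of withdrawn or terminated subjects", section 7.8 requires at least two years of follow-up after a device complication, and section 8.3 follows AEs to resolution or study end. These provisions should shrink the group, but none guarantees a performance evaluation.

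A third reply is that the loss would be visible: 10.4.1 reports numbers missing where relevant, 10.4.5 tabulates missing endpoint data by reason, and 10.4.10 lists individual data. That is right about event capture. It does not correct the denominator of a summary table. Section 10.1 permits a revised SAP before database lock, which gives an opportunity for the correction and does not make it.

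Three stronger conclusions that a reader might draw are not supported:

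- That every early leaver is lost from the pain VAS test because of 10.3. Those who leave before the Visit 6 score have no pair under any dataset.
- That only a blinded photographic rating admits a subject. A subject POSAS or satisfaction score at an exit visit could also do so.
- That 17 to 22 of 75 subjects is an upper limit on the loss. It is a planning allowance, and actual early loss could be anything from none upward.

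**Conclusion.** The point holds as a defect in the definition of the safety population. The literal text of 10.3 makes a performance evaluation a condition for safety analysis, it disagrees with the Protocol Summary, and 10.4.4 does not settle the matter.

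The consequence is conditional. It needs the literal reading to be applied, and treated subjects who leave before Visit 8 with no performance evaluation at exit. It biases the AE, serious AE, AE-withdrawal and response summaries in the device's favour only if those subjects had more events than the rest. The size cannot be derived from the documents and may be zero. In a study of at most 75 subjects, even one to three such withdrawals would turn 1.3% to 4.0% into 0% in the AE-withdrawal row. The effect on the VAS test is small under the assumptions shown: at most 0.16 cm. No performance inference changes. The correction should be made, with medium confidence that the ambiguity would affect the reported results.

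**What to change.** In 10.3, define two sets.

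- **Safety set:** all subjects who received at least one treatment, with no evaluation condition. Use it for every analysis in 10.4.4. The paired VAS test uses members with both the Visit 2 and Visit 6 values.
- **mITT set, performance only:** at least one treatment and at least one valid post-baseline assessment of the endpoint analysed. That means GAIS and MSS for the primary endpoint, as in 10.4.2, and the relevant scale for each secondary endpoint, as in 10.4.3. Tying the condition to the endpoint avoids admitting to the primary analysis a subject who has only an exit POSAS or satisfaction score.

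Name the safety set in 10.4.4, and reword the Protocol Summary sentence so that the all-treated rule applies to safety and the mITT rule to performance.

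The cost is one paragraph in 10.3, a phrase in 10.4.4 and one sentence in the summary. No new data are needed, since AEs are recorded from consent and VAS and response are recorded after each treatment. The change should be in place before database lock, so that the safety denominator is not chosen after the results are known.
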